## **Sensitivity Analysis**

The pre-specified sensitivity analysis will re-estimate the iNO effect on the primary outcome using GLM using a binomial distribution. Additional adjustment will be made for subgroups and any variables showing substantial imbalance across treatment arms at baseline. We assessed the balance of randomised groups on baseline and procedural characteristics using absolute standardised difference, defined as the absolute difference in means, mean ranks, or proportions divided by the pooled standard deviation. Baseline and procedural characteristics with absolute standardised difference  $>0.15$  ( $1.96 * \sqrt{1/330 + 1/330}$ ) were considered to be imbalanced and would be adjusted. The other way of exploring the potential imbalance across treatment arms will be achieved by constructing a logistic regression model to estimate the treatment effect and predictors of PPCs. Collinearity and overfitting will be assessed through Pearson's correlation tests and variation inflation factors. If outcome events are observed to be rare, a Poisson regression will be employed. Classic logistic regression will be performed with a consistent number of events, and the number of covariates in the model will be decided based on the number of outcomes. The ARISCAT score and operation duration score used as one randomization stratification will be treated as continuous variables, exploring their continuous impacts on the outcome.

Time-to-event (PPC) within the observation window (7 days and 30 days respectively) will be assessed using Kaplan-Meier curves and compared with log-rank tests. Per-protocol and as-treated analyses of PPCs will serve as sensitivity analyses. If a low missing rate (< 5%) in the primary outcome were presented, an extra sensitivity analyses with multiple imputations would be performed.

In addition to the standard analysis described above, the following analyses will be performed to test the robustness of the trial findings:

- (1) the count of positive component events within the composite will be assessed and groups will be compared using a Wilcoxon rank-sum test, and odds ratio with the 95% confidence interval will be assessed with a proportional odds logistic regression;
- (2) the effect of inhaled NO on each component will be analyzed using a GLM using Bonferroni correction for multiple comparisons with 99.37% Bonferroni-corrected confidence intervals reported ( $1 - 0.05/8 = 0.9937$ );
- (3) a multivariate analyses treating different components as a multiple outcome;
- (4) the average relative effect test will be conducted to determine if the average of component-specific treatment effects equals to zero and a distinct treatment effect is estimated for each component via GEE;
- (5) heterogeneity of treatment effect across components will be assessed by a treatment-by-component interaction test;

(6) patients in the treatment and control groups will be paired by risk profiles.

(7) The postoperative 30-day all-cause mortality will be combined with severity of PPCs scaled by Clavien-Dindo classification as a hierarchical composite outcome. This composite endpoint will be analyzed using prioritized generalized pairwise comparison methods, namely the win-ratio method/global rank sum technique [35]. Each patient from the intervention group will be compared to each patient in the placebo group (a total of  $m \times n$  comparisons where  $m$  is the total number of patients in the intervention group and  $n$  the number of patients in the standard care group) for the death endpoint and then on the Clavien-Dindo classification. Based on which patient performs better in each pair, the group they belong to would be declared the 'winner'. This would give us the total number of winners in each group and our test statistic would be based on this. In the case of the win-ratio method, for instance, the statistic would be the number of winners in the intervention group divided by the number of winners in the standard care/placebo group. This approach will allow us to infer if the intervention is significantly better than the standard care having taken into account the clinical priority i.e. treating mortality as a more important outcome than having a better Clavien-Dindo classification. This work will be reported separate to the main trial results.

(8) To enhance the interpretability of the results and provide valuable information for decision-making, the INORDINATE trial will employ

Acceptability Curve Estimation using Probability above Threshold (ACCEPT) analysis [36]. This analysis method involves calculating and plotting the probabilities of the true difference between treatments being above various acceptability thresholds, based on the data obtained from the trial. By using this approach, the limitations of traditional binary trial conclusions, which categorize results as either positive (meeting the trial aim) or negative (not meeting the trial aim), can be overcome. ACCEPT analysis provides a more nuanced understanding of the data and allows for a range of possible threshold values to be considered, thereby facilitating more informed decision-making.

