### **Baseline and intraoperative Characteristics**

Demographic, baseline, and intraoperative characteristics will be summarised using descriptive statistics and will be presented by treatment group. Categorical variables will be reported as counts and percentages. Percentages will be calculated according to the number of trial participants for whom data are available. Where values are missing, the denominator will be stated and no assumptions or imputations will be made. Continuous variables will be summarized in either means and standard deviation or medians and interquartile range, according to the distribution of the variables.

T-test or Wilcoxon rank sum test will be used for comparison of continuous data.  $\chi^2$  test or Fisher's exact test will be used for comparison of categorical data. Normality for continuous variables will be assessed via the Shapiro-Wilk normality test and visually using QQ-plots and residual plots. Appropriate variable transformation such as natural logarithm will be applied in case of non-normality. Should normality not be obtained through transformation of the

data, alternative non-parametric methods (such as Wilcoxon rank sum test) will be applied. All statistical tests will be 2-tailed with  $p < 0.05$  considered statistically significant. All analyses will be performed on an intention-to-treat basis.

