## **Primary Analysis**

The effects of inhaled NO on incidence of PPCs will be reported as number and percentages and estimated with risk ratio and 95% confidence intervals calculated with Wald's likelihood ratio approximation test and with Chi-squared or Fisher's exact test for hypothesis testing. The unadjusted analysis will estimate risk ratios with 95% confidence intervals by two-by-two table with the use of log-Normal approximation. In addition, the effect size will be expressed as risk differences (95% confidence intervals) with the number needed to treat as the reciprocal of the risk difference, rounded to the nearest integer. This will further be analysed as the generalised linear models (GLM) under binomial family with either log or logit link where appropriate. Odds ratios or relative risks together with 95% confidence intervals will be reported. Further adjustment on stratification variables such as ARISCAT index and time interval from infection to surgery will be made. The point estimates with 95% confidence intervals will be reported.

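### In the adjusted sensitivity analysis, extra covariates enter through a 5% test of baseline imbalance, so chance and not prognosis selects them and the model is not fixed in advance

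*SAP*

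**What the plan says.** The SAP plans adjustment at three points.

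- *Primary Analysis.* After the two-by-two comparison (chi-squared or Fisher's exact test) comes a binomial GLM, for which "Further adjustment on stratification variables such as ARISCAT index and time interval from infection to surgery will be made". These covariates are named in advance, and ARISCAT is itself a risk score for the primary outcome.
- *Sensitivity Analysis, first model.* The effect is re-estimated with a binomial GLM, and "Additional adjustment will be made for subgroups and any variables showing substantial imbalance across treatment arms at baseline". The screen is described as follows: "We assessed the balance of randomised groups on baseline and procedural characteristics using absolute standardised difference". Characteristics above 0.15 "were considered to be imbalanced and would be adjusted". The cut-off is written as 1.96 × sqrt(1/330 + 1/330). Being prognostic is not a condition, the screened variables are not listed, and the word for subgroups is not explained.
- *Sensitivity Analysis, second model.* Imbalance is also to be explored by "constructing a logistic regression model to estimate the treatment effect and predictors of PPCs". The predictors are not listed, and "the number of covariates in the model will be decided based on the number of outcomes".

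Separately, *Baseline and intraoperative Characteristics* plans significance tests between arms: "T-test or Wilcoxon rank sum test will be used for comparison of continuous data", with chi-squared or Fisher's tests for categorical data. *Pre-defined Subgroup Analysis* names ten variables: age, sex, cardiac or non-cardiac surgery, BMI, complexity, anaesthesia duration, smoking, one-lung ventilation, ARISCAT and the infection-to-surgery interval.

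**The concern.** A covariate is worth adjusting for because it predicts the outcome. Its observed difference between randomised arms is a poor guide to that, because for a variable fixed before randomisation any such difference is chance. A cut-off built from 1.96 standard errors turns the balance check into a significance test of a null hypothesis already known to be true. Its flags say nothing about prognosis: a variable unrelated to pulmonary complications is as likely to enter as a strong predictor, and a strong predictor that happens to be balanced is not brought in by this route.

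Two things are at stake. First, the SAP calls this analysis pre-specified, yet nobody can write down its covariates before seeing the data. Secondly, the sensitivity estimate may be less precise than one from a fixed prognostic list. The chance argument covers baseline variables only. Procedural characteristics, which the same screen includes, may be affected by treatment and raise a different question.

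**Working it through.** **Inputs from the SAP.** 330 per arm, 30% against 20%, 10% dropout (Sample Size Consideration); two-sided 5% level (Statistic significance and software); cut-off 0.15 (Sensitivity Analysis). With 10% dropout, 330 × 0.9 = 297 per arm remain.

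**Assumed, because the SAP does not give them.** The number of variables screened, their independence, and the prognostic strength of the covariates.

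**1. The SAP's cut-off.** 1.96 × sqrt(2/330) = 1.96 × 0.07785 = 0.1526, printed as 0.15. The figure is reproduced.

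**2. Chance that a randomised variable is flagged.** A standardised difference has standard error of about sqrt(2/n), so P(flag) = 2 × (1 − Φ(cut-off / sqrt(2/n))).

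- n = 330, cut-off 0.1526: z = 1.96, P = 5.0%.
- n = 330, cut-off 0.15: z = 0.15/0.07785 = 1.93, P = 5.4%.
- n = 297: P = 6.3% at 0.1526 and 6.8% at 0.15.

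**3. Several variables screened.** For k independent variables, the expected number flagged is k × p and P(at least one) = 1 − (1 − p)^k.

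| k (assumed) | Expected, p = 5.0% / 5.4% | At least one, p = 5.0% / 5.4% |
|---|---|---|
| 10 | 0.5 / 0.5 | 40% / 43% |
| 20 | 1.0 / 1.1 | 64% / 67% |
| 30 | 1.5 / 1.6 | 79% / 81% |

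**4. Effect on power.** Simulation with 297 per arm, 30% against 20%, and 4,000 trials per setting. There were five equally strong independent prognostic covariates and ten noise covariates, with logistic fits and a two-sided 5% Wald test. Two of the five prognostic covariates stand in for ARISCAT and the interval. The standard deviation of the prognostic linear predictor was assumed to be 0.7, 1.0 or 1.5.

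| Model | SD 0.7 | SD 1.0 | SD 1.5 |
|---|---|---|---|
| Unadjusted | 81.3% | 79.8% | 79.8% |
| Two fixed covariates | 82.6% | 82.3% | 83.3% |
| Two fixed plus those flagged at 0.15 | 82.3% | 82.7% | 84.1% |
| All five fixed | 84.0% | 85.9% | 90.2% |

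The third row is nearest to the SAP's model if no other covariates are forced in. Against the fixed list it gives up 84.0 − 82.3 = 1.7, 85.9 − 82.7 = 3.2 and 90.2 − 84.1 = 6.1 points. The trigger itself changes power by −0.3, +0.4 and +0.8 points over the two fixed covariates. The simulation error of each figure is about sqrt(0.83 × 0.17/4000) = 0.6 points.

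**5. Type I error.** With both arms at 30%, the two-fixed-plus-flagged model rejected in 4.4% to 5.2% of trials, and imbalance-only selection in 4.5% to 4.9%. Neither is inflated.

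**6. Events available for a fixed list.** 0.30 × 297 + 0.20 × 297 = 148.5.

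**The case against.** The strongest reply is that the rule does little. It is an addition to one sensitivity analysis. The adjusted model under Primary Analysis uses named strata, one of them a risk score for the outcome. The trigger is a fixed numerical rule, and Blinded Analysis has the primary analysis done on coded arms, which limits the scope for steering. The same sentence also adjusts for subgroups. If that means all ten listed variables, every obvious predictor is already in the model whatever its balance. Finally, when a flagged variable is prognostic, adjusting for it is useful.

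Most of this stands, and it rules out several stronger readings that a reader might infer:

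- *That covariates of the trial's adjusted analysis are chosen by imbalance instead of by prognosis.* Primary Analysis does not use the rule.
- *That the benefit of adjustment is lost, or that the sensitivity model gains no precision.* The part due to ARISCAT and the interval is kept, and with those two included the simulated power exceeds the unadjusted figure in every setting.
- *That the rule inflates type I error.* It does not.
- *That the baseline significance tests select covariates.* Selection uses standardised differences; the tests are a reporting matter.

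The reply does not rescue the trigger. Coded arms reduce bias in choosing covariates but do not fix the set. The subgroup wording can mean all ten variables, or only those subgroup variables that prove imbalanced, and the SAP does not say which. A prognostic variable that happens to be imbalanced is handled equally well by a list fixed beforehand, which also covers the balanced ones.

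**Conclusion.** The concern holds for the covariate-adjusted sensitivity analysis and no further. The 0.15 rule is a 5% test of baseline imbalance. It adds about 1 in 20 screened baseline variables by chance (5.0% to 5.4% at 330 per arm, 6.3% to 6.8% at 297), and it leaves the model open until the data are seen. The figure of 64% to 81% for at least one flag rests on an assumed 20 to 30 independent variables; correlated variables would change it.

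The cost in precision is modest and uncertain. About 2 to 6 points of power depends on assumed prognostic strengths and on five equally strong covariates. It would be smaller if ARISCAT carries most of the prognostic information, and little or nothing if all the listed subgroup variables are always included. The primary chi-squared or Fisher test and the sample size do not depend on it. This is a weakness of pre-specification that is cheap to mend, not a threat to the trial's main conclusion.

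**What to change.** In Sensitivity Analysis, delete the imbalance trigger and the undefined reference to subgroups. Name one closed list of covariates known before randomisation, all already in the SAP: ARISCAT as a continuous score, infection-to-surgery interval, age, sex, cardiac against non-cardiac surgery, and smoking history. Adjust for all of them whatever the observed balance. The full subgroup list should not simply be taken over, because anaesthesia duration is known only after treatment has begun. Use the same closed list for the second logistic model, or list its predictors separately.

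Keep standardised differences as a description of the arms. Preferably, also drop the hypothesis tests of baseline variables from Baseline and intraoperative Characteristics. This is secondary: those tests do not affect the model, but some P values below 0.05 will occur by chance and may be misread as failed randomisation.

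The cost is an SAP wording change, dated before the treatment codes are broken, and a few model parameters. With the interval in three categories the six covariates need seven terms, or eight with treatment. About 148.5/8 = 18.6 expected events per term support this comfortably.

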## **Randomization and Masking**

Eligible participants will be randomly allocated at 1:1 ratio to either NO inhalation or placebo. The randomization process will utilize permuted-block randomisation, with stratification based on the predicted risks of PPCs using the Assess Respiratory Risk in Surgical Patients in Catalonia (ARISCAT) index (< 45 [low and medium risk],  $\geq 45$  [high risk]), as well as the time interval from infection to surgery ( $\leq 10d$ , 11-28d, 29-49d). Random blocks of 4 or 6 will

be used for randomization. The allocation will be concealed by a web-based system that was accessed no earlier than the morning of the surgery.

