## **Intervention**

All participants will receive perioperative management based on our institutional standard practice, which includes various components such as preoperative evaluation and preparation, general anaesthesia with or without neuraxial anaesthesia and/or nerve blocks, mechanical ventilation, inotropic drugs and vasopressors, postoperative sedation and analgesia, diuretics, intravenous fluids, antibiotics and invasive monitoring. This management regimen will encompass a range of interventions and monitoring, including but not limited to non-invasive or invasive arterial pressure, electrocardiogram, central venous pressure, cardiac output, pulse oximetry, temperature, urine output, arterial blood gases, coagulation monitoring, and frequent routine laboratory examinations. No additional interventions or laboratory tests beyond the standard perioperative management will be conducted on participants. All perioperative management will be at the discretion of the treating anesthesiologist and in accordance with existing protocols for patients undergoing surgery and equal for both groups. Predicted body weight will be calculated as  $50 + 0.91 * (\text{height [cm]} - 152.4)$  for male and  $45.5 + 0.91 * (\text{height [cm]} - 152.4)$  for female. Patients will be randomized into one of the following interventions (Figure 1):

[figure not shown]
*Inhalation of NO:*

After randomization, patients assigned to NO group will receive NO inhalation at a concentration of 80 parts per million (ppm) through the respiratory circuit of a mechanical ventilator. The intervention will commence immediately after tracheal intubation and will persist until either extubation or the patient exits the operation room, whichever happens first.

*Placebo group:*

After randomization, patients assigned to placebo group will receive standard care and inhalation with the NO vehicle gas, aka nitrogen through the respiratory circuit of a mechanical ventilator. The intervention will commence immediately after tracheal intubation and will persist until either extubation or the patient exits the operation room, whichever happens first.

For the intervention details, please refer to the published protocol [34].

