## **Secondary Analysis**

Secondary outcomes will be analyzed according to the intention-to-treat principle. Proportion of patients experiencing secondary endpoints including 30-day all-cause mortality, unplanned ICU admission, thrombotic events (including deep venous thrombosis and pulmonary embolism), non-pulmonary complications (including stroke, cardiac infarction, ventricular dysfunction, delirium, acute kidney injury, surgical revision for bleeding, hypotension/hypertension, arrhythmia, hyper-responsiveness) will be compared using Fisher's exact test or Chi-squared tests depending on incidence rate. Each component of the thrombotic events and non-pulmonary complications will also be compared. The severity of PPCs scaled by

Clavien-Dindo classification will be treated as an ordinal variable; the ordinal regressions will be conducted. Postoperative length of hospital stay will be analysed using Kaplan-Meier curves and compared with log-rank tests. Cox proportional hazard models were utilized for length-of-stay outcomes, incorporating a shared frailty model. The proportionality assumption was visually inspected using Kaplan-Meier plots, log-log plots, and Schoenfield residuals, with no clear evidence of divergence. Non-parametric comparisons were made using Kaplan-Meier curves and between-group log-rank tests.

For continuous outcomes, linear or quartile regression was chosen based on the skewness of the distribution. Models were adjusted for the ARISCAT index and the time interval from infection to surgery as per randomisation strata, treated as fixed effects. Between-group risk differences were estimated and reported with 95% confidence intervals. Adverse reactions were documented and analyzed, with differences in incidence tested using Fisher exact tests. No Type I error corrections were conducted for multiple tests in this context.

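### The adjusted sensitivity model can admit covariates that arise under treatment, and the SAP wrongly names operation duration as a randomisation stratifier

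*SAP*

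**What the plan says.** Four statements in the SAP bear on this.

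- **Adjustment set, first statement (Sensitivity Analysis).** "Additional adjustment will be made for subgroups and any variables showing substantial imbalance across treatment arms at baseline".
- **Adjustment set, second statement (same paragraph).** Balance is assessed by absolute standardised difference, and "Baseline and procedural characteristics with absolute standardised difference" above 0.15 are to be adjusted for. Procedural is not defined and no covariate list is given.
- **Subgroup variables (Pre-defined Subgroup Analysis).** The ten variables include duration of anaesthesia in three bands, with no statement of whether this is planned or actual.
- **Stratification factors.** Sensitivity Analysis says: "The ARISCAT score and operation duration score used as one randomization stratification will be treated as continuous variables". Randomization and Masking gives the two factors as the ARISCAT index and, in its words, "as well as the time interval from infection to surgery". Primary Analysis agrees ("Further adjustment on stratification variables such as ARISCAT index and time interval from infection to surgery will be made"), and so does Secondary Analysis ("Models were adjusted for the ARISCAT index and the time interval from infection to surgery as per randomisation strata").

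On timing, the Intervention section says: "The intervention will commence immediately after tracheal intubation and will persist until either extubation or the patient exits the operation room".

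**The concern.** A balance check followed by adjustment corrects chance imbalance only when the variable was fixed before randomisation. For a variable measured while the gas is running, a difference between arms may itself be an effect of treatment. Adjusting for it then removes or adds part of the effect being estimated. A threshold on the observed difference makes this worse, because the variables most likely to cross it are those that treatment has shifted.

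The adjusted model is there to show that the primary result is robust. If its covariates include variables that arise under treatment, a departure from the primary estimate cannot be interpreted: it could be correction of chance imbalance or distortion of the effect. The interaction test for duration of anaesthesia has the same problem if the duration is actual. Because the section supports two readings (baseline only, or baseline plus procedural), whether procedural variables enter could also be settled after the data are seen.

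The stratifier sentence is a separate matter. It misdescribes the design. As written, the continuous-covariate analysis uses a variable that was not a stratifier and leaves out the continuous form of one that was.

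**Working it through.** **1. The plan's own threshold.** With 330 per arm (Sample Size Consideration), the standard error of a standardised difference is √(1/330 + 1/330) = 0.0778, and 1.96 × 0.0778 = 0.1526. The stated 0.15 reproduces.

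**2. What the threshold selects.** For a variable whose true shift between arms is d SD, the chance of being flagged is P(|N(d, 0.0778)| > 0.15).

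| True shift d (SD) | Chance of being flagged |
|---|---|
| 0 | 5.4% |
| 0.10 | 26.1% |
| 0.15 | 50.0% |
| 0.20 | 74.0% |
| 0.30 | 97.3% |

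Subgroup variables are adjusted for whether flagged or not.

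**3. Which variables arise under treatment.** The abstract places randomisation after induction of anaesthesia. The Randomization and Masking section says the allocation system is opened no earlier than the morning of surgery. On either account allocation precedes the gas. Type and complexity of surgery may be fixed by then. Intraoperative measurements and the actual duration of anaesthesia or operation are not.

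**4. What adjustment could do: an illustration.** The documents give no effect of NO on any procedural variable, so the shifts and odds ratios here are assumptions. The SAP supplies the PPC risks: 30% control, 20% NO.

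- Let X be N(0,1) in controls and N(d,1) under NO.
- Model: logit P(PPC) = α + β·NO + γX, with γ = ln 1.5 or ln 1.65.
- Solve α and β so that the marginal risks are exactly 0.30 and 0.20. The true total risk reduction is then 10.0 points in every row.
- Adjusted risk difference: the mean of expit(α + β + γx) − expit(α + γx) over the pooled distribution of X, half from each arm.

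Negative d is a favourable shift (towards lower PPC risk).

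| d (SD) | Adjusted reduction, OR 1.5 per SD | Adjusted reduction, OR 1.65 per SD |
|---|---|---|
| −0.3 | 7.81 points | 7.34 points |
| −0.2 | 8.54 | 8.23 |
| −0.1 | 9.27 | 9.11 |
| 0 | 10.00 | 10.00 |
| +0.1 | 10.73 | 10.88 |
| +0.2 | 11.45 | 11.77 |
| +0.3 | 12.18 | 12.65 |

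With no shift there is no bias. With a shift, the adjusted estimate moves up or down by about 0.7 to 2.7 points. For scale, the standard error of the risk difference is √(0.3·0.7/330 + 0.2·0.8/330) = 0.0335, or 3.3 points.

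**5. The stratification factors side by side.**

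| SAP section | Factors named |
|---|---|
| Randomization and Masking | ARISCAT (<45, ≥45); infection-to-surgery interval (≤10, 11–28, 29–49 days) |
| Primary Analysis | ARISCAT; infection-to-surgery interval |
| Secondary Analysis | ARISCAT; infection-to-surgery interval |
| Sensitivity Analysis | ARISCAT score; operation duration score |

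Three sections agree and the fourth differs. The interval is already defined in days under Computation of dates, so its continuous form is available. It is not lost from the plan, since it still enters through the primary adjustment and the subgroup variables.

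**The case against.** - **Procedural may mean only the type and complexity of surgery.** The Presentation of Data section pairs baseline characteristics with the procedures performed, and the SAP says intraoperative elsewhere when it means that. This reading is possible, and such variables could properly stay. But the term is undefined, and the reading does not cover duration of anaesthesia, which enters through the subgroup clause.
- **The bias figures are hypothetical.** Nothing in the SAP suggests that NO alters operative or anaesthetic duration, perioperative management is meant to be equal in both arms, and the shifts in the illustration are all smaller than one standard error of the risk difference. This stands, and it limits the weight of the point. A systematic shift does not average out as sampling error does, however, and a robustness check should not depend on NO having no effect on its covariates.
- **Planned or actual duration may be settled in the protocol, and uncorrected multiple tests are already called exploratory.** The first is possible, as the protocol is not at hand. The second concerns multiplicity and does not address adjustment for a variable arising after randomisation.
- **The numerical threshold limits choice after the fact.** It does. What stays open is whether procedural variables enter the screen at all.
- **The operation duration sentence is probably a drafting slip in a side analysis.** Probably so, but it contradicts three other sections and an analyst following the SAP strictly would carry it out.

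**Conclusion.** The concern holds and should be fixed. Naming operation duration as a stratification factor is an error as written. The adjustment rule is internally inconsistent and wide enough to admit variables that arise under treatment.

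The consequence is confined to the adjusted sensitivity estimate and, if duration is actual, the anaesthesia-duration subgroup. The unadjusted primary comparison and the stratifier-adjusted model are untouched.

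The textual contradictions are certain. The bias is conditional: nil if NO does not shift the variable, and up to about 2.7 points either way on a true 10-point reduction under the assumed shifts of up to 0.3 SD and odds ratios of 1.5 to 1.65 per SD.

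**What to change.** **Sensitivity Analysis.** Restrict both the imbalance adjustment and the subgroup adjustment to variables fixed before randomisation, and list them. Procedure descriptors known preoperatively, such as cardiac or non-cardiac surgery and complexity grade, may stay. Leave intraoperative variables to the descriptive reporting by arm already planned ("Demographic, baseline, and intraoperative characteristics will be summarised using descriptive statistics").

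**Stratifier sentence.** Reconcile it with Randomization and Masking, so that the continuous covariates are the actual stratification factors: the ARISCAT score and the infection-to-surgery interval in days.

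**Pre-defined Subgroup Analysis.** State whether duration of anaesthesia is planned or actual. Use planned duration if it was recorded before randomisation. Otherwise label this subgroup post-randomisation and exploratory, and keep it out of the adjustment set.

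**Cost.** SAP wording only. One of the ten subgroups is redefined or downgraded to exploratory, and data collection does not change.

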### Sample Size Consideration

The sample size for this study has been calculated based on the incidence of postoperative pulmonary complications of incidence of PPCs is reported to be approximately 20% for all surgical populations [62, 63] and increase up to 39.5% after COVID-19 infections[5]. The study assumes a 30% PPC incidence in the control group. We anticipate a 30% relative reduction (from 30% to 20%) in PPCs incidence for the iNO group. At 5% significance level and on consideration of 10% dropouts, the sample size needed to achieve 80% power is thus calculated to be 660 (330 per group) using a

two-sided Chi-squared test with continuity correction.

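### The SAP names Pearson correlations and variance inflation factors as its check for overfitting of the PPC logistic model, but these measure only collinearity and cannot show overfitting

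*SAP*

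**What the plan says.** The Sensitivity Analysis section of the SAP plans, as a further way of looking at imbalance between arms, "constructing a logistic regression model to estimate the treatment effect and predictors of PPCs". It then states the check: "Collinearity and overfitting will be assessed through Pearson's correlation tests and variation inflation factors". Shortly afterwards it adds a rule on model size: "the number of covariates in the model will be decided based on the number of outcomes". No events-per-parameter ratio and no covariate list accompany that rule.

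The same section also describes a binomial GLM in which "Additional adjustment will be made for subgroups and any variables showing substantial imbalance across treatment arms at baseline". Imbalance there means an absolute standardised difference above 0.15, so part of that list depends on the data.

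The SAP names no bootstrap or cross-validated optimism, calibration slope, shrinkage or penalisation. The section on statistical significance says that multiple tests are not corrected and will be treated as exploratory.

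**The concern.** Two different problems are assigned to one pair of tools, and the tools address only the first. Collinearity is a property of the covariates. Overfitting is a property of the fit: coefficients follow chance features of the outcome in this sample and come out too extreme. Covariates can be almost uncorrelated, with inflation factors near 1, while the model is badly overfitted.

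If the check is carried out as written, a low inflation factor would count as evidence on overfitting, although it carries none. What is at stake is how far the reported predictor coefficients can be trusted and, to a small degree, the adjusted NO estimate from this sensitivity model.

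**Working it through.** The plan gives no figure on this point to reproduce. The check is whether the named tools can register overfitting at the plan's own size and event rates.

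**Inputs from the SAP (Sample Size Consideration).** Assumed PPC rate of 30% on placebo and 20% on NO: "We anticipate a 30% relative reduction (from 30% to 20%) in PPCs incidence for the iNO group"; 660 patients, 330 per group; 10% dropout.

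**Expected events.**
- All 660: 330 × 0.30 + 330 × 0.20 = 99 + 66 = 165.
- After 10% dropout, 297 per arm: 297 × 0.30 + 297 × 0.20 = 89.1 + 59.4 = 148.5 of 594.

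**A plausible model size (an assumption, since the logistic model's list is not given).** The pre-defined subgroup factors comprise six binary factors (age, sex, surgery type, BMI, and smoking and one-lung ventilation taken as yes/no) and four three-level factors (complexity, anaesthesia duration, ARISCAT, infection-to-surgery interval). That is 6 + 4 × 2 = 14 parameters, or 15 with treatment. Events per parameter: 148.5 / 15 = 9.9, or 165 / 15 = 11.

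**What the tools use.** Pearson's r between covariates j and k uses only those two columns. The inflation factor is VIF_j = 1 / (1 − R²_j), where R²_j comes from regressing covariate j on the other covariates. The PPC outcome appears in neither formula.

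**Simulation 1 (660 patients, 30% v 20%, treatment plus k independent covariates with no effect, 200 runs per setting; performance re-measured in 6,600 new patients).** A calibration slope of 1 would mean no overfitting.

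| k | Events per parameter, 165/(k+1) | Largest VIF in any run | Mean of largest absolute r | Apparent AUC | AUC in new patients | Calibration slope |
|---|---|---|---|---|---|---|
| 5 | 27.5 | 1.03 | 0.08 | 0.60 | 0.56 | 0.62 |
| 10 | 15.0 | 1.06 | 0.10 | 0.61 | 0.55 | 0.46 |
| 15 | 10.3 | 1.06 | 0.11 | 0.63 | 0.55 | 0.34 |
| 30 | 5.3 | 1.10 | 0.13 | 0.66 | 0.54 | 0.20 |
| 60 | 2.7 | 1.19 | 0.14 | 0.71 | 0.53 | 0.10 |

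The slope falls from 0.62 to 0.10 while no VIF exceeds 1.2.

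**Simulation 2 (594 patients, AUC of the covariates alone, truth 0.50).** Repeated runs gave, at 15 covariates, an apparent AUC of 0.60 with a largest VIF of 1.08 to 1.09. At 30 covariates they gave an apparent AUC of 0.64 to 0.65 with a largest VIF of 1.13 to 1.17.

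**Effect on the NO estimate.** The true log odds ratio is ln[(0.20/0.80) / (0.30/0.70)] = ln(0.583) = −0.539.
- 15 covariates: overstated by about 2–4% across repeated runs. At 2.4% this is 0.024 × 0.539 = 0.013, against a standard error of 0.198. Coverage of the 95% interval was 95.5%.
- 30 covariates: overstated by about 5–8%. At 7.4% this is 0.074 × 0.539 = 0.040, against a standard error of 0.20. Coverage was 93.8%.

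**Chance of at least one covariate with p < 0.05.** Simulated at n = 594: 55% (k = 15) and 81% (k = 30). Expected from independent tests at 5%: 1 − 0.95^15 = 54% and 1 − 0.95^30 = 79%. The error rate per covariate was 5.0% to 5.5% for k from 10 to 30. These chances are therefore almost wholly multiplicity.

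**The case against.** The best defence is that this is one loosely worded clause in a sensitivity analysis that already has a guard. Tying the number of covariates to the number of outcomes is an events-per-variable rule in all but the ratio, and the total event count can be known without unblinding. The model's stated purpose is to examine imbalance, not to predict in new patients, and the SAP plans no AUC. The simulated covariates are independent noise, a worst case; real predictors would give less optimism.

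Much of this stands. The plan is not without protection against overfitting, AUC matters only if discrimination is reported, and the simulated optimism is an upper illustration. What does not fall is the core point. A rule on model size does not assess the fitted model, and the tools named for that assessment carry no information on it, whatever the covariates. The model is also meant to name predictors of PPCs, so the stability of their coefficients matters.

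A reader might take the 55% and 81% chances of a false predictor as the harm done by overfitting. The arithmetic does not support that: they are what 15 or 30 tests at 5% produce, and the SAP already treats uncorrected multiple tests as exploratory. Nor would a cap of one parameter per 10 events remove them. With 13 covariates plus treatment the chance is still about 50% (1 − 0.95^13 = 49%).

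**Conclusion.** The point holds as a minor one: the stated check for overfitting is wrong for its purpose and would pass an overfitted model. At 15 null covariates and 594 patients, the largest inflation factor is at most about 1.1 while apparent AUC is 0.60 against a true 0.50. The simulated sizes rest on assumed covariate counts and independent covariates with no effect; the conclusion about the tools does not.

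A reader might also infer that the trial's main result or the adjusted NO effect is at risk. The document does not support this. The primary hypothesis test is a chi-squared or Fisher test that does not use this model, and the adjusted log odds ratio moves by about 2–4% at 15 covariates with coverage near 95%. Nor does the SAP promise a statement that overfitting was absent; it only names the means by which overfitting would be judged.

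**What to change.** In the Sensitivity Analysis section:

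1. Restrict Pearson correlations and variance inflation factors to collinearity.
2. Assess overfitting by the bootstrap optimism-corrected calibration slope, repeating any data-driven covariate selection in each resample. Add the optimism-corrected AUC only if discrimination is reported.
3. Before unblinding, fix the covariate list and a maximum number of parameters, set from the blinded total event count. As an illustration, one parameter per 10 events would allow about 14 at 148 events or 16 at 165. The cap limits model size but does not replace step 2: the simulated slope was already 0.46 at 15 events per parameter.
4. Label any predictors of PPCs as exploratory, in line with the SAP's own statement on multiple tests.

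The cost is a few sentences and a standard bootstrap in R on existing data. The one small downside is that reported model performance will look less favourable.
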